### Statistical Methods and Sample Size

The trial will follow a  $k$ -stage single arm design with  $k=2$ , being an extension of Simon's 2-stage design. In this design with  $k=2$ , there are two analyses: a single interim and a final analysis. At the interim, the response rate is evaluated in a fixed number ( $m$ ) of patients using a predefined decision rule to determine if the study should stop for futility (in the situation where the null is confirmed) or for efficacy (in the situation where the alternative hypothesis is confirmed). If neither hypothesis is confirmed, a further fixed number of patients ( $l$ ) are assessed for response and a final analysis is performed on all ( $m+l$ ) patients. In both interim and final analyses, the response rate will be presented together with the associated exact 90% confidence interval (CI).

The rationale for a null hypothesis of  $p_0=0.20$  is based on previously published analysis from a clinical trial with pembrolizumab (KEYNOTE-012) in 32 patients with metastatic TNBC (27 patients were evaluable), where an ORR of 18.5% has been observed for pembrolizumab monotherapy. These patients were relatively heavily pre-treated PD-L1 positive patients, with over 50% having received 3 or more lines of therapy.

The ORR of pembrolizumab in combination with BGB324 is expected to be at least as high as this in patients unselected for PD-L1 positive disease.

With  $p_0=0.20$  and  $p_1=0.35$ , the interim will be conducted with  $m=28$  evaluable patients who have the potential for at least 24 weeks (that is, at least 2 on treatment scans) of follow-up. If 5 or fewer responses are observed in up to 28 patients, the trial will be terminated in favor of the null

for futility; however, if 11 or more responses are observed, then the trial will be stopped in favor of the alternative for demonstration of activity. Otherwise, up to a further 28 patients may be evaluated, for a maximum total of 56 evaluable patients. The full study population will have the potential for at least 24 weeks of follow-up. If a total of 17 or more responses are seen in up to 56 patients, then the null will have been rejected in favor of the alternative; otherwise the null will not have been rejected.

Up to 56 evaluable patients may therefore be enrolled to this clinical trial. It is expected that approximately 75 patients will be screened in order to identify 56 patients who meet all the inclusion and exclusion criteria and who are evaluable for response.

An evaluable patient is defined as one who has received at least one dose of pembrolizumab and BGB324, and has measurable disease, as determined by the investigator site at baseline.

Demographic and clinical characteristics at entry will be summarized using appropriate descriptive statistics. PD-L1 and Axl expression will be summarized.

Further details on the statistical methods and sample size can be found in [Section 8.1](#).

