Further tumor imaging will be performed in all patients every 9 weeks for the first 46 weeks and then 12-weekly thereafter until progression (which may be confirmed). On each occasion, tumor assessments will include imaging of the chest, abdomen and pelvis. Additional anatomy, including brain and bone, should be imaged based on signs and symptoms of individual patients. Disease response will be evaluated at these time points according to RECIST 1.1. If either or both of the study treatments are stopped for any reason other than confirmed progression, tumor imaging will continue every 12 weeks until confirmed progression.

Patients who are suspected of having a complete or partial response will have their response confirmed at the next scheduled assessment or no earlier than 4 weeks (28 days) later.

Blood sampling for PBMC and Axl signaling and inhibition biomarker analysis will be performed at Screening, Cycle 1, Days 4 and 8 and every study visit thereafter until Cycle 9, Day 1.

Blood sampling for BGB324 pharmacokinetic (PK) analysis will be performed on blood samples taken on:

- Cycle 1, Days 1 and 3 as follows: pre-dose and at 2, 4, 6 and 8 hours post dose;
- Cycle 1, pre-dose on Days 2, 4, 8 and 15;
- Cycles 2 and 3, pre-dose (study days 22 and 43 respectively).

Blood sampling for future pembrolizumab PK analysis will be performed on blood samples taken pre-dose on Cycle 1, Days 1 to 4, 8 and 15 and then pre-dose at Cycles 2 and 3 (study days

22 and 43 respectively). These samples will be frozen and stored centrally for future reference and analysis.

Patients with tumor amenable to repeat sampling may have additional fresh biopsies taken on up to 2 occasions post-dose at time points agreed between the Investigator and the patient. Where possible, efforts will be made to obtain follow up biopsy material where a patient has responded to treatment or has progressed on treatment.

Further details on sample collection and handling for all PK and biomarker assessments are described in the Laboratory Manual.

Patients who discontinue BGB324 treatment (for reasons other than disease progression) may be able to continue with (monotherapy) pembrolizumab until 106 weeks (that is, 35 completed cycles of pembrolizumab). These patients will no longer be required to have the following assessments from 6 weeks after the discontinuation of BGB324 (unless clinically indicated):

- ECG;
- Echocardiogram (or Multi Gated Acquisition Scan (MUGA));

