- ~ Physical examination
- ~ Clinical chemistry
- ~ Hematology
- ~ Coagulation
- ~ Urinalysis

- ~ ECG (triplicate test; pre-dose)
- ~ BGB324 oral dosing 200 mg (consecutive daily dosing 21 day cycle)
- ~ PK sampling BGB324 (pre-dose)
- ~ PK sampling for storage (pre-dose) - pembrolizumab
- ~ Adverse events
- ~ Concomitant medication

Cycle 2-35 (every 3 weeks), Day 1

- ~ ECOG PS
- ~ Vital signs
- ~ Physical examination
- ~ Clinical chemistry
- ~ Hematology
- ~ Coagulation
- ~ Urinalysis (performed on Cycle 2 Day 1 only)
- ~ Pregnancy test (if applicable)
- ~ Thyroid function tests (performed at Cycles 3, 5, 7, 9, 11, 13, 15, 17 only in Year 1 and then Cycles 19, 21, 23, 25, 27, 29, 31, 33, 35 in Year 2)
- ~ Echocardiogram (or MUGA) (performed at Cycles 9 and 17 in Year 1 and then Cycles 25 and 33 in Year 2)
- ~ ECG (triplicate test; pre-dose)
- ~ Tumor imaging (performed at Cycles 4, 7, 10, 13, 16, 20, 24, 28, 32 or Weeks 10, 19, 28, 37, 46, 58, 70, 82, 94, 106, and then every 12 weeks until progression)
- ~ Disease assessment (performed at Cycles 4, 7, 10, 13, 16, 20, 24, 28, 32 or Weeks 10, 19, 28, 37, 46, 58, 70, 82, 94, 106, and then every 12 weeks until progression)
- ~ Tumor biopsy (up to 2 optional post treatment biopsies)
- ~ Biomarkers (performed only at Cycles 2-9)
- ~ Pembrolizumab 200 mg fixed dose (infusion)
- ~ BGB324 dosing 200 mg (daily oral dosing 21 day cycle)
- ~ PK sampling BGB324 (pre-dose Cycles 2 and 3 only)
- ~ PK sampling - pembrolizumab (pre-dose Cycles 2 and 3 only)
- ~ Adverse events
- ~ Concomitant medication

Post Treatment Visit (only after both treatments are discontinued in either Year 1 or Year 2)  
+30 days from last dose of study treatment(s)

- ~ ECOG PS
- ~ Vital signs
- ~ Physical examination
- ~ Clinical chemistry
- ~ Hematology
- ~ Coagulation

- ~ Urinalysis
- ~ Thyroid function tests
- ~ ECG (triplicate test)
- ~ Adverse events
- ~ Concomitant medication
- ~ Tumor imaging (where applicable – for example, to confirm progression)
- ~ Disease assessment (where applicable – for example, to confirm progression)
- ~ Tumor biopsy (optional) at progression

Follow-Up (if the patient has had a Post Treatment visit in Year 1 or Year 2) - every 12 weeks

- ~ Concomitant medication (where applicable)
- ~ Tumor imaging (where applicable; every 12 weeks until disease progression)
- ~ Disease assessment (where applicable; every 12 weeks until disease progression)
- ~ Subsequent anti-cancer treatment

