## 8 DATA EVALUATION: CRITERIA FOR EVALUATION OF OBJECTIVES

### 8.1 Statistical Considerations, Interim Analysis and Sample Size

The study will employ a  $k$ -stage single arm design, an approach derived from basic statistical theory. If  $p$  denotes the true tumor response rate with drug, the null and alternative hypotheses to be assessed in this trial are:  $H_0 : RR=p_0$  vs  $H_1 : RR=p_1$  ( $p_0 < p_1$ ), with  $p_0=0.20$  and  $p_1=0.35$ . To test these hypotheses, this trial is a  $k$ -stage single arm design with  $k=2$ , being an extension of Simon's 2-stage design. In this design with  $k=2$ , there are two analyses: a single interim and a final analysis. At the interim, the response rate is evaluated in a fixed number ( $m$ ) of patients using a predefined decision rule to determine if the study should stop for futility (in the situation where the null is confirmed) or for efficacy (in the situation where the alternative hypothesis is confirmed). If neither hypothesis is confirmed, a further fixed number of patients ( $l$ ) are assessed for response and a final analysis is performed on all ( $m+l$ ) patients. In both interim and final analyses, the response rate will be presented together with the associated exact 90% confidence interval (CI).

With  $p_0=0.20$  and  $p_1=0.35$ , the interim will be conducted with  $m=28$  patients. If 5 or fewer responses are observed in these 28 patients, the trial will be terminated in favor of the null for futility; however, if 11 or more responses are observed, then the trial will be stopped in favor of the alternative for demonstration of activity. Otherwise a further 28 patients may be evaluated, for a total of 56 patients. If a total of 17 or more responses are seen in 56 patients, then the null will have been rejected in favor of the alternative; otherwise the null will not have been rejected.

Based on 500,000 trial simulations, this design provides an overall power of 80.6% to test the stated null and alternative hypothesis with a 1-sided Type I error rate of 0.048. Under the null hypothesis, the probability of correctly stopping for futility at the interim is 50.2% and, under the alternative hypothesis, the probability of correctly stopping for activity at the interim is 38.4%. Consequently, the expected sample size for the design is 42-44 subjects.

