**Table 20: RECIST 1.1 evaluation and definitions of disease response**

Complete Response (CR)	Disappearance of all TLs since baseline. Any pathological lymph nodes selected as TLs must have a reduction in short axis to <10 mm.
Partial Response (PR)	At least a 30% decrease in the sum of the diameters of TLs, taking as reference the baseline sum of diameters
Stable Disease (SD)	Neither sufficient shrinkage to qualify for PR nor sufficient increase to qualify for PD
Progression of disease (PD)	At least a 20% increase in the sum of diameters of TLs and an absolute increase of at least 5 mm, taking as reference the smallest sum on study (this includes the baseline sum if that is the smallest on study).
Not Evaluable (NE)	Only relevant if any of the TLs were not assessed or not evaluable or had a lesion intervention at this visit. Note: if the sum of diameters meets the progressive disease criteria, progressive disease overrides not evaluable as a TL response

All patients who are considered to have had a complete or partial response must have this response confirmed by a confirmatory scan at least 4 weeks later.

Details of any new lesions will also be recorded with the date of assessment. The presence of one or more new lesions is assessed as progression, however, in the absence of clinical deterioration, treatment can continue. The suspected disease progression should be confirmed after 28 days.

A lesion identified at a follow up assessment in an anatomical location that was not scanned at baseline is considered a new lesion and will indicate disease progression.

The finding of a new lesion should be unequivocal: i.e., not attributable to differences in scanning technique, change in imaging modality, or findings thought to represent something other than tumor.

If a new lesion is equivocal, for example because of its small size, the treatment and tumor assessments should be continued until the new lesion has been confirmed. If repeat scans confirm there is a new lesion, then the progression date should be declared using the date of the initial scan.

Disease progression requires confirmation. The confirmatory scan should occur preferably at the next scheduled visit and no earlier than 4 weeks after the initial assessment of progression of disease (PD) in the absence of clinical deterioration.

The overall visit response will be derived using the algorithm shown in [Table 21](#).

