## 8.6 Completion and Closure of the Study

The study will be completed when either:

- The study is terminated at the interim analysis following the DRC review of the ORR and risk/benefit for all patients included in the interim analysis. In this (early termination) situation a Clinical Study Report will be written. The interim analysis will occur once 28 evaluable patients have had the potential to be followed for at

least 24 weeks. In this situation, the last patient, last visit (LPLV) will occur at this point.

*OR*

- The study will complete and the final analysis will occur once all patients (planned 56 evaluable patients) have had the potential to be followed for at least 24 weeks. The last patient, last visit (LPLV) will occur at this point. All data will be reconciled and the database will be locked for analysis. These data will be included in the CSR.

Assuming that there are patients continuing on study treatment at the date of LPLV, the study will be closed once all patients have completed their last dose of study drug or discontinued study drug and have completed their post treatment visit.

- If this closure date occurs after the date of LPLV, only serious safety data will be collected between LPLV and the final closure date. An addendum (or addenda) to the CSR will be generated to report any outstanding serious safety data.
- If this ‘closure date’ occurs before the date of LPLV (because every patient has stopped their study treatment, for example), the study will close at the same time as the date of LPLV.

Study start is defined by the first patient to enter screening, however, the First Patient In (FPI) is when the first patient receives the first dose of study drug.

LPLV is defined as the last visit after all evaluable patients who have had the potential to be followed for at least 24 weeks and includes all data for the final analysis of all evaluable patients.

Study Completion is defined by the date of the LPLV i.e. after the planned number of evaluable patients have had the potential to be followed for at least 24 weeks.

Study Closure is defined by completion of the last dose of study drug and post treatment visit i.e. when the last patient has completed the last dose of study drug or discontinued for any reason and been followed up to the Post Treatment Visit. This date will either be the same as the date of Study Completion or later in time.

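### The 24-week minimum follow-up allows confirmation of a response first seen at Week 19 only if an unscheduled scan is done; the protocol also lets the site wait for Week 28, after the cut-off

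*Protocol*

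**What the plan says.** **Cut-off.** The synopsis (Statistical Methods and Sample Size) places the interim at 28 "evaluable patients who have the potential for at least 24 weeks (that is, at least 2 on treatment scans) of follow-up". Sections 8.2.2 and 8.3 repeat the 24 weeks and the two scans for the interim. Section 8.3 ties the final database lock to 24 weeks of potential follow-up, and Section 8.6 puts LPLV at the same point, both for a stop at the interim and for the final analysis.

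**Scans.** Section 5.1.1 schedules imaging at "Weeks 10, 19, 28, 37, 46, 58, 70, 82, 94, 106", and footnote 7 to Tables 4 and 5 gives a window of 7 days either side.

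**Confirmation.** Section 8.5 (below Table 20) says that patients considered to have a CR or PR "must have this response confirmed by a confirmatory scan at least 4 weeks later", and the synopsis makes the same demand. On timing, the synopsis (Study Procedures and Assessments) says that patients with a suspected response "will have their response confirmed at the next scheduled assessment or no earlier than 4 weeks (28 days) later". Section 5.3.10 adds that scans should be done as appropriate to confirm a response. Section 8.11, which defines the primary analysis, words confirmation as an expectation and not as a requirement.

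**After the cut-off.** If patients are still on treatment at LPLV, Section 8.6 states that "only serious safety data will be collected between LPLV and the final closure date".

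**Decision rule (Section 8.1).** The null response rate is 0.20 and the alternative 0.35. Futility: "If 5 or fewer responses are observed in these 28 patients". Activity: "if 11 or more responses are observed, then the trial will be stopped in favor of the alternative". At the final analysis, 17 or more responses in 56 patients reject the null.

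**The concern.** The 24 weeks are justified by counting scans, and confirmation is not mentioned in that justification. For a patient with only the minimum follow-up, a response first seen at the second of the two promised scans may have no confirmatory scan yet, although the site has followed the protocol.

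The primary endpoint is a count judged against boundaries at 5/6, 10/11 and 16/17, so one patient can change the decision. If unconfirmed responses are not counted, the observed ORR is biased downwards and a wrong futility stop becomes more likely. If they are counted, the result includes responses that do not meet the requirement in Section 8.5.

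Responses first seen at scan 2 are plausible here. Section 8.5.1 expects some responses to come later than with cytotoxics, or after an initial increase in tumor burden. Sections 4.1 and 8.11 allow later scans to be used for ORR where early progression may have been false.

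**Working it through.** **1. Calendar.** The start of Week N is N − 1 weeks after Day 1 (study days 22 and 43 are Weeks 4 and 7).

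| Event | Weeks after Day 1 | With the ±1-week window |
|---|---|---|
| Scan 1 (Week 10) | 9 | 8–10 |
| Scan 2 (Week 19) | 18 | 17–19 |
| Extra scan 28 days after scan 2 | 18 + 4 = 22 | 21–23 |
| Minimum follow-up | 24 | – |
| Scan 3 (Week 28) | 27 | 26–28 |

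The 28-day route ends inside 24 weeks. The scheduled route ends 2 to 4 weeks after it. Because 24 weeks is a minimum, only patients dosed in roughly the last 2 to 4 weeks of accrual to each analysis are exposed.

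**2. The plan's own figures.** Let X and Y be independent Bin(28, p).

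- P(futility stop) = P(X ≤ 5)
- P(activity stop) = P(X ≥ 11)
- P(reject) = P(X ≥ 11) + P(6 ≤ X ≤ 10 and X + Y ≥ 17)

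Exact enumeration, with the Section 8.1 figure in brackets:

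- power 80.5% (80.6%)
- one-sided type I error 4.8% (0.048)
- futility stop at 0.20: 50.1% (50.2%)
- activity stop at 0.35: 38.4% (38.4%)
- expected sample size 41.6 under the null and 44.1 under the alternative (42–44)

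The stated figures are reproduced. The exact chance of a wrong futility stop at 0.35 is 3.9%.

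**3. Effect of unconfirmed responses, if they are not counted.** Suppose k late patients per stage each have a share g of their true responses unconfirmed at the cut-off. A late patient then counts with probability p(1 − g), so the observed count in a stage is Bin(28 − k, p) + Bin(k, p(1 − g)). Stage 1 responses missed at the interim are added back at the final analysis; stage 2 losses are not. The expected loss per stage is k × p × g.

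The documents give neither k nor g. I take g = (share of responses first seen at scan 2) × (share confirmed only at Week 28). The scenarios below are assumptions, evaluated at p = 0.35.

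| k per stage; share at scan 2 | Expected loss per stage, all sites wait | Power, all wait | Wrong futility stop, all wait | Type I error (p = 0.20), all wait | Power, half wait | Wrong futility stop, half wait |
|---|---|---|---|---|---|---|
| none | 0 | 80.5% | 3.9% | 4.8% | 80.5% | 3.9% |
| 2; 20% | 2 × 0.35 × 0.20 = 0.14 | 79.4% | 4.4% | 4.5% | 80.0% | 4.2% |
| 4; 30% | 4 × 0.35 × 0.30 = 0.42 | 76.8% | 5.5% | 3.9% | 78.7% | 4.7% |
| 5; 40% | 5 × 0.35 × 0.40 = 0.70 | 74.1% | 6.7% | 3.4% | 77.5% | 5.2% |

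If all sites wait, correct activity stops at the interim fall from 38.4% to 36.3%, 32.0% and 28.0%.

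**The case against.** **Week 28 is not the only confirming scan.** A reader might infer that 24 weeks is too short by construction. The documents do not support that. The synopsis, footnote 7 and Section 5.3.10 together allow a scan from 28 days, at 21 to 23 weeks, so 24 weeks can hold two scans and a confirmation. This objection stands, and it turns a certain loss into a possible one. It does not close the gap, because nothing requires the earlier scan before the cut-off and waiting is expressly allowed.

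**Several conditions must coincide.** The response must be first seen at scan 2, in a late-enrolled patient, at a site that waits, in an analysis that rejects unconfirmed responses. Section 8.3 leaves missing-data rules for the primary endpoint to the SAP, which is not at hand. If pending responses count, the modelled power loss disappears. This also stands. What remains in the protocol itself is the difference in force between Sections 8.5 and 8.11.

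**The interim is not mechanical.** Under Section 8.2.2 the DRC also weighs safety and quality of response, so it could take account of a PR awaiting confirmation, and stage 1 responses are recovered if the trial continues. This softens the interim risk. It does not help the last stage 2 patients, or any patient after a futility stop.

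**Any cut-off leaves the last scan unconfirmed.** At 28 weeks the same could be said of responses first seen at Week 28. That is true, but the plan promises two scans, and it is reasonable that a response on either of them can be confirmed by either permitted route.

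**Conclusion.** The point holds as a gap in timing that is cheap to close, not as an error in the design. A protocol-compliant site can leave a Week 19 response in a late-enrolled patient unconfirmed at the interim or final analysis, and Section 8.6 then collects no further efficacy data after LPLV.

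Under the assumed scenarios the cost is about 1 to 6 percentage points of power if all sites wait for Week 28, and about 0.5 to 3 points if half do. Wrong futility stops rise from 3.9% to at most 6.7%. These sizes rest on assumed numbers of late patients and late responses, and on unconfirmed responses not being counted.

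Two stronger readings should be avoided. The stated power and type I error are not wrong; they are reproduced exactly or nearly so. Nor does this mechanism favor a false claim of activity: missing responses lowers the type I error.

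**What to change.** **Preferred.** In the synopsis and Sections 8.2.2, 8.3 and 8.6, define the interim, LPLV and final cut-off as potential follow-up through the Week 28 scan including its window, that is, 28 weeks. This adds about 4 weeks (28 − 24) to the recruitment pause and to the time to final analysis. It needs no added patients and no scans beyond those already scheduled.

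**Alternative.** Keep 24 weeks, and state that for a response first seen at Week 19 the confirmatory scan already allowed from 28 days is to be obtained before the cut-off. The cost is an earlier scan in the few patients concerned.

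**In either case.** Align Section 8.11 with the synopsis and Section 8.5 on whether only confirmed responses count towards ORR.

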### Schedules of Assessment and Pembrolizumab Administration Timing

**Table 3** summarizes the timing of pembrolizumab administration up to cycle 35 (approximately 24 months of treatment) in relation to the timing of disease assessment.

**Table 4** summarizes the schedule of assessments in Year 1 and **Table 5** summarizes the schedule of assessments in Year 2.

